There will be two groups that participants can be assigned to if they choose to participate in the study. Each person will be randomly assigned to one of these groups. One group will provide information about PrEP and HIV prevention and referral to PrEP clinics in the community. The second group will be the same as the first group but will also provide access to a CHW who will assist them with getting to a PrEP clinic and also helping them with other needs they may have.

A member from the study team will review the informed consent documents with the prospective participants and ask them questions to make sure they are eligible to participate in this study (PrEP-LINK eligibility and demographic screening form). Their responses to the prescreen form will not be shared with anyone outside of the study and will not contain any identifying information. They will be kept completely private, and will be in a password protected, encrypted database on a secured server at UAMS that can only be accessed by designated study staff.

Before we collect this information, we ask that participants provide their name so that we can assign a 9-digit study-ID number to de-identify their responses. Names will be stored separately from responses in locked filing cabinet in a secured office and will never be connected. At the end of the study, the link between the name and the study ID will be permanently destroyed.

Random Assignment to Study Condition. Once qualified for the study, we will randomly assign them to one of the two study groups. Once assigned to a group, after the completion of the

Table 4: Points of Contact for each Assessment for Aims 2 and 3

Type of Visit	Assessment	Location
Eligibility Screen	Education and Screening for initial PrEP indication including HIV rapid testing or self-report of recent negative HIV test within correctional facility	Pulaski County Jail, Central Arkansas Community Corrections Center, East Central Arkansas Community Corrections Center, Hidden Creek Opportunity Center, Quality Living Center, Better Community Development, Inc.
Consent, Enrollment	Baseline Research Assessment	CED Core community site
Presentation at PrEP Program for PrEP prescription dispensed	Baseline Research Assessment	Community based PrEP Provider
PrEP intervention sessions	Adherence assessment (self-report only), sexual risk ACASI, post-incarceration issues and HIV risk only	Community based PrEP provider or CED Core Community site

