 - If they decide to initiate PrEP, they will be prescribed PrEP medications by a physician in accordance with routine clinical care at their local PrEP clinic in the community.

Title: Linking High-Risk Jail Detainees to HIV pre-exposure Prophylaxis: PrEP-LINK

PI: [name]

Site: University of Arkansas for Medical Sciences

Only participants who test negative for HIV on their rapid test will be eligible to participate in the study. Individuals in the jail with a preliminary positive HIV test result will be immediately referred to the jail medical division, operated by TurnKey, Inc. for confirmatory testing.

Individuals tested in the community will be immediately referred to the Arkansas Department of Health for confirmatory testing.

- A baseline assessment survey (SEE: PrEP-LINK Baseline Battery) to be used during all 3 data collection time points (baseline, 6-month and 12-month)
 - The baseline assessment survey will ask questions about education, job status, criminal justice history, substance use, sexual behaviors, and other behaviors which may put individuals at risk for HIV, in addition to questions on knowledge and interest in PrEP.
 - The baseline assessment survey includes the following measures and it to be used in both **Specific Aims 2 & 3**:

Measure Name	Citation	Baseline Battery Page Number	Notes
PrEP-LINK Cover Sheet	Compiled for this study by the PIs	1	For internal tracking purposes
Demographics	Compiled for this study by the PIs	2-5	
Criminal Justice Involvement History	Compiled for this study by the PIs	5-6	
Health Insurance	Compiled for this study by the PIs	6	
HIV Sex Risk Perception	Compiled for this study by the PIs	7	
Income (ASI Lite)	McLellan, A.T., Luborsky, L., O'Brien, C.P. & Woody, G.E. (1980). An improved diagnostic instrument for substance abuse patients: The Addiction Severity Index. Journal of Nervous & Mental Diseases , 168, 26-33	8-9	
PrEP Knowledge (PrEP Knowledge Scale, RADAR)	Parsons, J. T., Rendina, H. J., Lassiter, J. M., Whitfield, T. H., Starks, T. J., & Grov, C. (2017). Uptake of HIV pre-exposure prophylaxis (PrEP) in a national cohort of gay and bisexual men in the United States: the motivational PrEP cascade. Journal of acquired immune deficiency syndromes (1999), 74(3), 285.	10	

Title: Linking High-Risk Jail Detainees to HIV pre-exposure Prophylaxis: PrEP-LINK
 PI: [name]
 Site: University of Arkansas for Medical Sciences

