The preliminary efficacy of the intervention will be determined by assessing the primary outcome of PrEP uptake by looking at the medical charts of the participants. A secondary outcome will be PrEP adherence defined by participants who were adherent to the medication determined by self-report at 3, 6, and 12 months. Following intent-to-treat (ITT) principles, all

Title: Linking High-Risk Jail Detainees to HIV pre-exposure Prophylaxis: PrEP-LINK

PI: [name]

Site: University of Arkansas for Medical Sciences

randomized participants will be included in data analyses. Standard bivariate analytic techniques, such as Spearman rank-order correlations, odds ratios, and Fisher's exact tests, will be used to assess preliminary associations between the intervention and each measure of PrEP uptake and to identify factors associated with the outcomes. Generalized linear regression models will be informed by these bivariate analyses.

In addition, we will test the randomization process by comparing the baseline demographic and confounding variables of the participants in each arm with Fisher's exact test for dichotomous variables, chi-square tests for nominal variables, *t*-tests for normally distributed continuous variables, and Wilcoxon signed-rank tests for non-normally distributed continuous variables, with statistical significance determined at alpha ≤ 0.05 . Any variable for which randomization does not result in equal proportions in each arm will be incorporated into the multiple-regression models as a potential confounding variable. Attrition effects will be evaluated by testing whether systematic differences exist between those participants who complete the research versus those who drop out. Thus, we can determine any potential bias introduced by attrition from the study.

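### The baseline check names a paired test for two independent arms, its covariate rule is not tied to the stated 0.05, and no covariate of the adjusted uptake model is fixed in advance

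*Combined protocol and SAP*

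**What the plan says.** Under Study Design and Procedures, allocation is individual: "Each person will be randomly assigned to one of these groups". No matching or pairing is described anywhere, and no allocation ratio is given.

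The Data Analysis section checks the randomisation by "comparing the baseline demographic and confounding variables of the participants in each arm". Dichotomous variables get Fisher's exact test, nominal ones chi-square, normal ones a t-test, and the rest "Wilcoxon signed-rank tests for non-normally distributed continuous variables, with statistical significance determined at alpha"; the sentence ends by setting that alpha at 0.05 or less. The sentence after it is the covariate rule: "Any variable for which randomization does not result in equal proportions in each arm will be incorporated into the multiple-regression models", as potential confounders.

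The preceding paragraph opens a second route. Bivariate methods, including odds ratios and Fisher's exact test, "will be used to assess preliminary associations between the intervention and each measure of PrEP uptake" and "to identify factors associated with the outcomes". Then: "Generalized linear regression models will be informed by these bivariate analyses".

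Neither these paragraphs nor the later one on generalised linear models names a covariate, and the link function is left open. The confounding variables to be tested are not listed. The battery table introduced by "The baseline assessment survey includes the following measures" has 22 entries besides the cover sheet.

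**The concern.** Three separate matters sit close together.

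- **The test.** Signed-rank works on within-pair differences, and this design has no pairs. The baseline check cannot be carried out as written for skewed variables.
- **The entry rule.** It speaks of equal proportions, mentions neither a p-value nor a tolerance, and does not say what balance means for a continuous variable. The analyst has to decide whether the 0.05 of the preceding sentence governs it.
- **Covariate choice.** Both routes into the model depend on the observed data. One reacts to chance differences between arms whatever their prognostic value; the other looks at the outcome.

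Uptake of PrEP is a primary outcome, and the Specific Aims say that the results will inform a later multi-site trial. Two analysts following this section could carry forward different adjusted estimates, and neither model could be shown to have been chosen beforehand.

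**Working it through.** **Inputs.** Arm sizes are assumed: 55 v 55 (about 110 in Aim 3, Specific Aims, split equally) or 40 v 40 (Power Calculations). The number of candidate variables k is not stated; 5 to 30 is an assumed range. Control uptake 0.50 and the 0.26 difference are from Power Calculations.

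**The plan's own figure.** With 40 per group and one-tailed 0.05, pooled-variance z = (0.26 × √40 − 1.645 × √(2 × 0.63 × 0.37)) / √(0.50 × 0.50 + 0.76 × 0.24) = 0.79, so power is 0.786, close to the stated 80%. The present point does not rest on it. It supplies the true odds ratio used below: (0.76/0.24)/(0.50/0.50) = 3.17.

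**Signed-rank on independent arms.** At 54 v 56 the test does not run. In one simulated skewed data set at 55 v 55, 2,000 arbitrary pairings gave p from 0.12 to 1.00 (rank-sum 0.38). In another, at 50 v 50, they gave 0.001 to 0.21, with 69% at or below 0.05 (rank-sum 0.030).

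**Rule read as p ≤ 0.05.** The chance of at least one flag among k independent variables is 1 − (1 − size)^k. At size 0.05 this is 0.226 for k = 5 and 0.785 for k = 30. At the actual size of Fisher's test at 55 v 55 (0.0198 to 0.0310) it is 0.095 to 0.611. Correlation lowers these. With 20 non-prognostic binary candidates about 0.6 enter; type I error is 0.051 (55 per arm) and 0.058 (40), and the median OR 3.24 and 3.27. With 20 normal candidates type I error is 0.044 to 0.054, or 0.048 to 0.055 using both routes. Unadjusted type I error in the binary-candidate simulations was 0.044 to 0.060, so there is no visible inflation.

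**Rule read literally.** P(exactly equal proportions) = Σ b(x; n, p)². For prevalence 0.1 to 0.5 this falls from 0.128 to 0.076 at 55 v 55 and from 0.150 to 0.089 at 40 v 40, so nearly every binary variable enters. Logistic model, Wald test, 6,000 trials per setting:

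| k | entered (55 / 40 per arm) | type I error | median OR (true 3.17) |
|---|---|---|---|
| 5 | 4.6 / 4.5 | 0.054 / 0.053 | 3.43 / 3.50 |
| 10 | 9.1 / 9.0 | 0.062 / 0.062 | 3.60 / 3.84 |
| 20 | 18.2 / 17.9 | 0.076 / 0.085 | 4.30 / 5.07 |

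An independent rerun at k = 20 gave type I error 0.070 / 0.082 and median OR 4.22 / 4.92. With a linear risk-difference model instead, type I error was 0.044 / 0.053 and the median estimate 0.263 / 0.259 for a true 0.26.

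**Power.** 4,000 trials, 20 independent normal covariates of which one is prognostic; control uptake 0.50, intervention uptake 0.75 (OR 1.6 per SD) or 0.72 (OR 2.7 per SD). Simulation error of a single figure near 0.7 is √(0.7 × 0.3/4000) = 0.007.

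| per arm, OR per SD | unadjusted | balance rule | both routes | fixed list, has the covariate | fixed list, misses it |
|---|---|---|---|---|---|
| 55, 1.6 | 0.781 | 0.764 | 0.760 | 0.792 | 0.775 |
| 55, 2.7 | 0.660 | 0.644 | 0.709 | 0.740 | 0.664 |
| 40, 1.6 | 0.650 | 0.618 | 0.617 | 0.660 | 0.643 |
| 40, 2.7 | 0.545 | 0.522 | 0.561 | 0.600 | 0.528 |

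The balance rule alone costs 0.016 to 0.032 against unadjusted. A fixed list holding the right covariate gains 0.031 to 0.043 over the two-route selection. A list that misses it loses 0.045 and 0.033 at OR 2.7 and gains 0.015 and 0.026 at OR 1.6.

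**A list of the kind suggested under the fix** (setting plus four risk-group/sex categories; category sizes and effects assumed): against unadjusted, power changes by −1 to +6 points; against the balance rule, by +2 to +7. If the variables are not prognostic, there is no gain over unadjusted.

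**The case against.** The best defence is that the section can be read sensibly. A reader might infer that the entry rule has no usable threshold. The text does not support that: 0.05 is set for these same comparisons in the sentence immediately before, and testing at 0.05 would serve no purpose if exact equality were the criterion. This stands. What remains is that the rule does not refer to that level and uses a term that does not fit a continuous variable.

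A reader might also infer that the signed-rank slip is what leaves the covariates open. It is not. With rank-sum and an explicit 0.05, covariates would still be picked from the data. The slip touches only skewed continuous baseline variables, and with unequal arms it would show itself at the first run. With equal arms it would run and return a meaningless p-value.

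Further, the fixed list is not uniformly better. Selection on outcome associations can find a strong prognostic variable that a list misses, as the OR 2.7 rows show. This also stands and belongs among the costs of the fix.

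Finally, the unadjusted odds ratio and Fisher's test of arm against uptake are already planned and depend on none of this. The section calls the efficacy results preliminary, and Power Calculations puts acceptability and feasibility first. That limits the harm but does not make the named test right or settle which covariates are used.

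**Conclusion.** The point holds in limited form and should be corrected. The named test is wrong for this design. The covariate rule is loosely worded. Independently of both, no covariate of the adjusted uptake model is fixed in advance.

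On the natural reading the consequence is small: type I error about nominal, median OR about 3.2 to 3.3 for a true 3.17, 2 to 3 points of power lost by the balance rule alone, and room for analyst discretion.

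A reader might infer that the plan inflates type I error and exaggerates the effect. That does not hold in general. Type I error of about 0.08 and a median OR of 4.2 to 5.1 need the literal reading, about 20 candidates and a logistic model together. The documents give neither the number of candidates nor the link. With 5 candidates the effect almost disappears, and a risk-difference model shows no such bias. Nor does the point undermine the planned unadjusted comparison.

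All sizes rest on assumed equal arms of 55 or 40, assumed numbers of candidates and assumed covariate effects. That signed-rank does not fit two unpaired arms, and that no covariate is named, rests on the text alone.

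**What to change.** In the Data Analysis section:

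1. Replace *signed-rank* with *rank-sum (Mann-Whitney)* wherever a between-arm baseline test is kept, or report baseline by arm descriptively without tests.
2. Delete the rule that adds covariates on observed imbalance.
3. Before the data are seen, name a short list of covariates already collected and expected to be prognostic for the adjusted uptake model. An example is recruitment setting (jail v community corrections or re-entry) and one coarse, non-overlapping risk-group/sex variable (MSM; PWID not MSM; other men; other women). The sponsor should choose the list, since the documents do not show which variables are prognostic.
4. Keep the unadjusted comparison and state whether it or the adjusted result leads.
5. Label models built from bivariate outcome associations as exploratory.

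The cost is wording only; no new data are needed. The downside is that a chance imbalance in an unlisted variable is handled only in a sensitivity analysis. If the list misses a strong prognostic variable, power can also be a few points below the planned two-route selection: about 0.66 v 0.71 at 55 per arm and OR 2.7 per SD.

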Trauma (Traumatic Life Events Checklist)	Based on Life Events Checklist by: Gray, M., Litz, B., Hsu, J., & Lombardo, T. (2004). Psychometric properties of the Life Events Checklist. Assessment , 11, 330-341. doi: 10.1177/1073191104269954v Weathers, F.W., Blake, D.D., Schnurr, P.P., Kaloupek, D.G., Marx, B.P., & Keane, T.M. (2013). The Life Events Checklist for DSM-5 (LEC-5). Instrument available from the National Center for PTSD at www.ptsd.va.gov	31-32	
Depression (Patient Health Questionnaire – 9 item version for Depression Symptoms)	Kroenke, K., Spitzer, R. L., & Williams, J. B. (2001). The Phq-9. Journal of general internal medicine , 16(9), 606-613.	33	
Discrimination (Major Experiences of Discrimination Scale)	Williams, D.R., Yu, Y., Jackson, J.S., & Anderson, N.B. (1997). Racial differences in physical and mental health: Socioeconomic status, stress, and discrimination. Journal of Health Psychology , 2(3), 335 -351	34-37	
Healthcare Access	National Health Interview Survey(CDC, 2018)	38-42	
Health and Utilization	RAND-36 Item Health Survey, ASI Lite, Medial Mistrust Survey, Commonwealth survey, survey on Disparities in quality of Health Care 2001	43-44	
Medical Mistrust	Medical Mistrust Index v2.2	45-47	
Social Support (Multidimensional Scale of Perceived Social Support)	Zimet, G.D., Dahlem, N.W., Zimet, S.G. & Farley, G.K. (1988). The Multidimensional Scale of Perceived Social Support. Journal of Personality Assessment , 52, 30-41.	48	
Civic Engagement	Compiled for this study by the PIs	49	

- HIPAA Authorization Form

Title: Linking High-Risk Jail Detainees to HIV pre-exposure Prophylaxis: PrEP-LINK

PI: [name]

Site: University of Arkansas for Medical Sciences

- This will be completed at baseline to allow the research team to collect medical records at the end of participation in the intervention regarding when participant first started taking PrEP medication and how often participant took PrEP medication.
- The following will be collected from the PrEP Clinic during participation in the study (12 months).
 - When participant first started taking PrEP medication for HIV prevention
 - How often participant took PrEP medication for HIV prevention
- Medical Records Release (HIPAA Release of Information to UAMS)

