Maintaining Contact. Because the study will take place over about 12 months after the participant's enrollment date, it will be important for us to be able to keep in contact with them. During each visit, we will ask for information that will help us contact them in the community in order to schedule study related appointments. We will ask for many ways to try to reach the participant's in case their phone number is disconnected or changed. We will contact them regularly to update your contact information. Participants will be considered to have missed a 6 or 12 month assessment 60 days after the target assessment date, and will be eligible 30 days before target assessment date. Research staff will make at least 3 contact attempts to reach participants for the 3 month and 9 month locator check in, with the goal of updating contact information.

Study Population

Participants will be enrolled in the proposed PrEP-LINK intervention who are HIV-uninfected and detained in the Pulaski County jail or individuals who are within 30 days of having been released from a correctional setting. We will work with jail staff to identify individuals who are within 2 weeks of discharge and will conduct screenings among these individuals to determine study eligibility. We will also work with Central Arkansas Community Corrections and local re-entry centers to identify individuals who have been released from incarceration within 30 days. Because many types of HIV related risks are present in this population (e.g. MSM or PWID), we will recruit participants from the following groups: MSM, PWID and heterosexual non-substance users (more participants may be enrolled, as needed). For the final two categories, (PWID and heterosexuals), we will recruit equal numbers of men and women. The recruitment will be completed when 120 individuals have been consented to have 100 participants complete the protocol.

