The primary analysis will compare uptake of PrEP by looking at the medical charts of the participants and self-reported behaviors of PrEP usage at the 3, 6, and 12 month visits between the study arms. Changes in self-reported adherence (verification with clinical chart abstraction, including lab tests for serum levels of medications), sexual behavior adjustment, post-incarceration contextual variables, and substance use will also be examined. Moreover, group differences in PrEP uptake, time-to-uptake, and number of PrEP clinic appointments kept will be compared. All analyses will use two-tailed tests of significance, with significance at alpha = 0.05. We will use generalized linear models with properly chosen link functions to analyze longitudinal data for each study aim. These models will be estimated with generalized estimating equations that use robust standard error estimates^{57,58}; they provide an extension of regression analysis to the case of correlated or repeated observations and allow for the inclusion of categorical and count-dependent variables and for appropriate modeling of covariance structures when observations are correlated across time.

Power Calculations. Because this is a pilot study, the primary emphasis will be on the acceptability and feasibility of the two arms; hence, power is limited to determine efficacy of the intervention. We used GPower⁵⁹ software to estimate the difference in proportions between the two groups, with respect to PrEP-LINKage, that could be detected with 80% power. Given 40 participants per group (total $n = 80$), one-tailed alpha = .05, and a proportion of 0.5 for the control group, we will have 80% power to detect a 0.26 difference in proportions between groups.

Ethical Considerations

This study will be conducted in accordance with all applicable government regulations and University of Arkansas for Medical Sciences research policies and procedures. This protocol and any amendments will be submitted and approved by the UAMS Institutional Review Board (IRB) to conduct the study.

Title: Linking High-Risk Jail Detainees to HIV pre-exposure Prophylaxis: PrEP-LINK

PI: [name]

Site: University of Arkansas for Medical Sciences

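### Comparing completers with dropouts cannot settle attrition bias, and no missing-data method backs the promise to analyse everyone randomised

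*Combined protocol and SAP*

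**What the plan says.** All of the analysis text is in the Data Analysis section of the combined protocol and SAP.

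- **Analysis population.** Under intention-to-treat, all "randomized participants will be included in data analyses".
- **Attrition.** "Attrition effects will be evaluated by testing whether systematic differences exist between those participants who complete the research versus those who drop out". The variables and the test are not named. The conclusion drawn is "Thus, we can determine any potential bias introduced by attrition from the study".
- **Outcomes.** Preliminary efficacy rests on "assessing the primary outcome of PrEP uptake by looking at the medical charts of the participants". The primary analysis adds "self-reported behaviors of PrEP usage at the 3, 6, and 12 month visits between the study arms". Adherence is defined by self-report.
- **Model.** Fisher's exact tests and odds ratios are listed for uptake. For longitudinal data the plan gives generalised linear models: "These models will be estimated with generalized estimating equations that use robust standard error estimates".

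Elsewhere, Study Population says: "The recruitment will be completed when 120 individuals have been consented to have 100 participants complete the protocol". Maintaining Contact defines when a 6- or 12-month assessment counts as missed. On the HIPAA authorisation for chart access, the plan says: "This will be completed at baseline to allow the research team to collect medical records at the end of participation in the intervention". The separate medical records release is obtained only once the participant has chosen a PrEP provider.

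No section gives a missingness assumption, imputation, weighting, a rule for people without a chart, or a sensitivity analysis for missing outcomes.

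**The concern.** Attrition bias in the arm comparison arises when those who are not observed differ, within arm, in the outcome that was not recorded. Comparing completers with dropouts on what was recorded can suggest that this might be so. It cannot measure the bias in the arm effect, and a non-significant result does not show that bias is absent. The plan treats it as settling the question.

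The second gap is how the promise to analyse everyone is kept. A GEE fitted to follow-up visits uses the visits that took place. Someone with no follow-up visit supplies no response, and without weighting or imputation is simply absent. The fit is then valid in general only if missingness is completely at random or depends only on covariates in the model.

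Arm-related dropout is plausible. The community health worker is expected to be in touch with intervention participants at least weekly, while controls receive information and referral. If retention is tied to PrEP use differently in the two arms, the self-reported comparison could be biased and still be reported as checked. The results are meant to inform a multi-site trial.

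**Working it through.** **1. The plan's own figures.** It states none for attrition bias. Its one power figure (Power Calculations: 40 per group, 0.50 versus 0.76, one-tailed alpha 0.05, 80%) reproduces:
- pooled: (0.26 − 1.645 × √(2 × 0.63 × 0.37/40)) / √((0.25 + 0.1824)/40) = 0.79, power 78.6%
- unpooled: 0.26/√((0.25 + 0.1824)/40) − 1.645 = 0.86, power 80.4%

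That figure is not in dispute here.

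**2. Implied loss.** 120 consented for 100 completing gives 20/120 = 16.7%. Applied to about 110 randomised, roughly 92 remain and 18 are lost. Assuming 1:1 allocation (55 per arm), that is about 46 and 9 per arm.

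**3. Power of the completer/dropout test.** Exact two-sided Fisher test at 0.05, for a characteristic held by 50% of completers and 30% of dropouts (assumed):

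| Completers vs dropouts | Power |
|---|---|
| 100 vs 20 | 34% |
| 92 vs 18 | 30% |
| 80 vs 30 | 41% |
| 46 vs 9 (one arm) | 12% |

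**4. Bias with equal retention in both arms.** Assume true PrEP use of 50% in both arms and 83.3% retained in each. In the control arm retention is unrelated to use. In the intervention arm it is 95% for users and 71.7% for non-users.
- Intervention, observed: 0.5 × 0.95 / (0.5 × 0.95 + 0.5 × 0.717) = 0.475/0.833 = 0.57
- Control, observed: 0.50
- Spurious difference: +0.07

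Swapping the arms gives −0.07. With 72.7% retained (90% and 55.5% in the intervention arm) it is 0.45/0.727 − 0.50 = +0.12.

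**5. Simulated GEE.** Unweighted logistic GEE, 110 people, month-6 and month-12 visits, no true effect, 1,000 runs per setting. The difference is at month 12; results are independence / exchangeable working correlation.

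| Dropout mechanism | Bias | Type I error | Mean number contributing |
|---|---|---|---|
| Completely at random | 0.003 / −0.002 | 5.6% / 5.0% | 92 / 92 |
| Depends on month-6 outcome (intervention arm) | 0.020 / 0.006 | 4.1% / 5.9% | 110 / 110 |
| Depends on unobserved month-12 outcome (step 4 rates) | 0.063 / 0.069 | 9.2% / 10.5% | 92 / 92 |

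In the last setting a completer/dropout comparison on a baseline variable was significant in 3.7% and 2.9% of runs. That variable was generated independently of the outcome, so this shows what happens when the recorded variable carries no information about dropout. It is not the detection rate of every possible check.

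**6. What the missing data alone allow.** With 55 per arm:

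| Missing per arm | Observed | Difference | Missing = no PrEP | Worst to best case |
|---|---|---|---|---|
| 9 | 23/46 vs 35/46 | 0.26 | 12/55 = 0.22 | 3/55 = 0.05 to 21/55 = 0.38 |
| 15 (80 analysed) | 20/40 vs 30/40 | 0.25 | 10/55 = 0.18 | −5/55 = −0.09 to 25/55 = 0.45 |

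**7. Size against sampling error.** In step 4 the 95% half-width is 1.96 × √(0.50 × 0.50/46 + 0.57 × 0.43/46) = 0.20, so a bias of 0.07 is about a third of it.

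**The case against.** **The analysis is inferred from silence.** A reader might infer that the plan specifies unweighted GEE on available data and therefore keeps neither of its promises. The documents do not say that. Neither term appears, and the firm defect is that no missing-data method is named. GEE is also not always biased, as the first two settings in step 5 show.

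**Chart uptake is better protected.** Missing a research visit need not mean losing the uptake outcome, because chart authorisation is signed at baseline and charts could be sought for people who drop out. This stands, with a limit: the provider-specific release comes only after a clinic is chosen, and nothing says how a person with no chart is counted.

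**Some people without follow-up still enter the model.** The battery is given at baseline, 6 and 12 months, and the plan examines changes. Where baseline is a response row, such a person is included. This stands too. The point is therefore confined to outcomes analysed at follow-up only, as in the primary comparison of self-reported PrEP use and in adherence.

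**Differential retention is assumed.** Both arms have the same payments, locator check-ins and contact attempts, and the research assistant collects follow-up data. That is fair; the patterns above are illustrations.

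**The attrition check is not limited to baseline variables.** The plan speaks of systematic differences, so charts could allow a comparison on uptake as well. That would still not reach self-reported outcomes that were never recorded.

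**It is a pilot.** Power Calculations puts the emphasis on acceptability and feasibility and admits limited power for efficacy. This limits the consequence but does not make the attrition sentence correct.

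**Conclusion.** The point holds in limited form and should be corrected. The claim that the comparison determines attrition bias is wrong as written. It is descriptive, has roughly 12% to 41% power for a 20-point difference at the sizes considered, and cannot detect bias that depends on unobserved outcomes. The promise to include everyone randomised has no method behind it for self-reported outcomes analysed at follow-up only.

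The size is not determined by the documents. Under the assumed patterns a null effect appears as about +7 or +12 points, or −7 with the arms swapped; other patterns give little or none.

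Three stronger conclusions are not supported:
- **That chart-based uptake is biased by missed visits.** This would require uptake to be lost together with the visit, which the baseline authorisation may prevent.
- **That the plan expects 27% attrition.** The figure 1 − 80/110 = 27.3% combines the power calculation with the Aim 3 total; the plan never calls 80 the expected completers. Even 16.7% starts from people consented across Aims 2 and 3, so some of that loss may precede randomisation.
- **That the plan will produce a biased arm effect.** That depends on retention patterns nobody yet knows.

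**What to change.** 1. Replace the attrition sentence with a statement that the completer/dropout comparison is descriptive, will be reported by arm, and does not rule out attrition bias.
2. Seek charts for all randomised participants regardless of visit attendance, using the baseline authorisation, and report chart ascertainment by arm.
3. For self-reported outcomes, state a missing-at-random assumption and use multiple imputation before GEE, or inverse-probability-weighted GEE, with arm and baseline battery variables.
4. Present no chart or missing = no PrEP as one sensitivity analysis, alongside best/worst-case or delta-type bounds, and not as the only coding. It can create bias of its own. Suppose true uptake is 50% in both arms, 30% of controls and 15% of intervention participants have no chart obtained, and 30% of those people did start PrEP. Coding them as not started gives 0.50 − 0.30 × 0.30 = 41.0% and 0.50 − 0.15 × 0.30 = 45.5%, a false 4.5-point benefit. Charts could be found more often in the intervention arm, because the community health worker helps people reach a clinic.

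Cost: some extra analysis and possibly slightly wider intervals. The baseline battery is already collected and chart abstraction is already planned.
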